### **C. Outcome**

The outcome of the event must be recorded accurately and classified into one for the following categories:

- Recovered/Resolved.
- Recovered/Resolved with sequelae.
- Recovering/Resolving.
- Not recovered/Not resolved.
- Fatal.

### **D. Severity**

When describing the severity of an AE the terms mild, moderate, or severe should be used. Clinical judgment should be used when determining which severity applies to any AE.

If the severity of an AE fluctuates day-to-day, e.g., a headache or constipation, the change in severity should not be recorded each time; instead, only the worst observed severity should be recorded with AE start and stop dates relating to the overall event duration, regardless of severity.

A severe AE is not the same as a SAE. For example, a participant may have severe vomiting, but the event does not result in any of the SAE criteria above. Therefore, it should not be classed as serious.

The severity of an AE will be recorded as one of the following:

- **Mild:** easily tolerated, does not interfere with normal daily activities, does not require intervention
- **Moderate:** causes some interference with daily activities; minimal, local, or noninvasive intervention indicated
- **Severe:** daily activities limited or completely halted; intervention indicated.

### **E. Causality**

See [Section 12.4](#) above.

### **F. Action Taken with Study Medication**

This question refers to the action taken with the study intervention due to an AE. The action with the study intervention must be classed as:

- Dose Increased.
- Dose Not Changed.
- Dose reduced.
- Drug interrupted.
- Drug Withdrawn.
- Not Applicable.

## 12.6. Follow-up Procedures for Adverse Events

The investigator may be asked to provide follow-up information to the sponsor for any reported AEs or during the investigation of potential safety issues. Such requests for additional safety information may occur after the safety follow-up visit (i.e., after the study).

Adverse events considered related to the study intervention by the investigator or the sponsor should be followed up until resolution or the event is considered stable.

It will be left to the investigator's clinical judgment whether an AE is of sufficient severity to require the participant's removal from treatment. A participant may also voluntarily withdraw from treatment due to what he or she perceives as an intolerable AE. Further details of withdrawal are presented in [Section 10](#). If either of these occurs, the participant should proceed to an ET visit and be given appropriate care under medical supervision until symptoms cease or the condition becomes stable. If a safety concern is identified following withdrawal of a participant, the sponsor may contact the investigator for additional follow-up information.

## 12.7. Potential Cases of Drug-Induced Liver Injury

All investigational sites are required to submit to the sponsor the laboratory results for any participant after randomisation that meets the criteria for the selected laboratory parameters as follows:

- ALT or AST  $> 3 \times \text{ULN}$  with the appearance of fatigue, nausea, vomiting, right upper quadrant pain or tenderness, fever, rash, and/or eosinophilia ( $> 5\%$ ).
- ALT or AST  $> 8 \times \text{ULN}$ .
- ALT or AST  $> 5 \times \text{ULN}$  for more than 2 weeks.
- ALT **or** AST  $> 3 \times \text{ULN}$  **and** (TBL  $> 2 \times \text{ULN}$  or INR  $> 1.5$ ).

These reports must be sent to the sponsor via email for SAE reporting within 24 hours of becoming aware of the results. In addition, please send a copy of the participant's baseline laboratory results with all reports to the sponsor. Sponsor contact details are provided in the trial centre file ([APPENDIX 2](#)).

Abnormal values in AST and/or ALT concurrent with abnormal elevations in TBL that meet the criteria outlined above are considered potential cases of drug-induced liver injury and will be considered as protocol-defined criteria for withdrawal and

important medical events. The investigator will arrange for the participant to return to the investigational site as soon as possible (within 24 hours of notice of abnormal results) for repeat assessment of ALT, AST, TBL, INR, % eosinophils, alkaline phosphatase, and GGT levels, detailed history, and physical examination. Participants should be followed in this way until all abnormalities have normalised (in the investigator's opinion) or returned to the baseline state. However, if the above transaminase elevation criteria are confirmed by the first set of follow-up laboratory tests, the participant must permanently discontinue the study intervention.

Elevations in ALT **or** AST  $> 3 \times$  ULN **or** TBL  $> 2 \times$  ULN alone are not considered potential cases of drug-induced liver injury, but will be followed as detailed above, within 72 hours' notice of abnormal results. If the participant cannot return to the investigational site, repeat assessments may be done at a local laboratory and the results sent to the sponsor.

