### **3.5. Benefit/Risk Assessment**

Cannabidiol oral solution has been approved for use in treatment of seizures associated with LGS, DS, and TSC. [REDACTED]

[REDACTED]

Participants in the current study may experience some improvement of symptoms and will receive comprehensive clinical exams and clinical monitoring associated with the study. The risks of participation are primarily associated with adverse reactions to GWP42003-P, although there may also be some discomfort from collection of blood samples and other study procedures. Cannabidiol oral solution contains 79 mg/mL ethanol. In this study in young children, there may be a potential risk of accumulation when CBD-OS is chronically coadministered with other medicines containing ethanol or other substrates for alcohol dehydrogenase (such as propylene glycol). Clinical judgment should be used weigh potential benefit from CBD-OS against this potential risk. More information about the known and expected benefits, risks, and reasonably anticipated AEs associated with GWP42003-P may be found in the current approved version of the Investigator's Brochure (IB) (CBD-OS IB).

The most commonly reported side effects include somnolence; decreased appetite; diarrhoea; transaminase elevations; fatigue, malaise, and asthenia; rash; insomnia, sleep disorder, and poor-quality sleep; infections; pyrexia; and vomiting. Serious side effects include hepatocellular injury, somnolence and sedation, suicidal behaviour and ideation, and hypersensitivity reactions. Further information is included in the latest CBD-OS IB.

Overall, the extensive clinical safety and efficacy results of GWP42003-P were demonstrated across 5 Phase 3 studies, an open-label study, and the expanded access program in the treatment of paediatric epilepsy syndromes. And it is believed that GWP42003-P has a favourable benefit risk profile for the treatment of seizures associated with TSC, DS, and LGS in the participant age ranges being investigated in this study.

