#### 8.1.2. Dose Escalation and Dose Adjustments

The 52-week treatment period includes a fixed 2-week titration schedule followed by flexible dose optimisation. The optimal dose will be based on the participant's observed efficacy, safety, and tolerability per the investigator's clinical judgement.

On Day 1 (Visit 3) of treatment with GWP42003-P, participants will initiate the fixed 2-week titration of GWP42003-P, beginning with a dose of 5 mg/kg/day (2.5 mg/kg b.i.d.). On Day 8 ( $\pm$  3 days), the dose will be increased to the target dose level of 10 mg/kg/day (5 mg/kg b.i.d.). Participants will be observed on Day 15 (Visit 5).

After Day 15 (Visit 5), the GWP42003-P dose may be escalated further based on individual clinical response and tolerability using a flexible titration schedule, per the investigator's clinical judgement. If, in the investigator's opinion, the participant is experiencing a clinically meaningful improvement in seizures, investigators will have the option to maintain or increase a participant's dose at any time during or between scheduled visits until EOT. Doses may be increased up to a maximum of 20 mg/kg/day (10 mg/kg b.i.d.) for LGS and DS or 25 mg/kg/day (12.5 mg/kg b.i.d.) for TSC, in maximum weekly increments of 5 mg/kg/day ( $\leq$  2.5 mg/kg b.i.d.). If possible, changes in dose should be avoided during the 3 days prior to PK visits or before PK samples have been collected on the day of PK study visits (as specified in [APPENDIX 1](#)) unless clinically indicated for safety ([Section 9.1.10.1](#) provides additional details).

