e Where possible, urine samples for biochemistry will be analysed at the site's local laboratory by use of a dipstick with any relevant findings being sent for further urinalysis (urinalysis, microscopy, culture, and sensitivity, as applicable).

All laboratory results will be reviewed, and the reports signed and dated by an investigator. Any results considered to be of clinical significance must be documented as AEs and followed up as clinically appropriate.

All laboratory results considered to represent an AE must be documented on the eCRF. For reporting and follow-up of potential cases of drug-induced liver injury, see [Section 12.6](#).

Repeat samples will be taken, if required, for clinical follow-up or if the sample is lost or damaged. Any abnormal EOT clinical laboratory result of clinical significance must be repeated at regular intervals until it returns to normal, or until an investigator is satisfied that the abnormality is not related to the study intervention and needs no further investigation.

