### **10.1. Discontinuation of Study Intervention**

- Parent(s)/LAR may decline to continue participating in study intervention and/or other protocol-required therapies or procedures at any time during the study.
- Parent(s)/LAR who choose to discontinue participating in study intervention and/or other protocol-required therapies or procedures should not be automatically removed from the study. Whenever safe and feasible, and in agreement with the sponsor, the participants should remain in the study to ensure safety surveillance and/or collection of outcome data.
- The investigator is to discuss with the participant's parent(s)/LAR the appropriate processes for discontinuation from study intervention or other protocol-required therapies. The investigator must discuss with the participant's parent(s)/LAR the possibilities for continuation of activities described in the SoA ([APPENDIX 1](#)) and must document this decision in the eCRF.
- These participants should complete an ET visit followed by 10-day taper period if clinically indicated (i.e., if no safety reasons prohibit continued treatment; refer to [Section 8.1.2](#)). A safety follow-up visit should be conducted 4 weeks after the participant's last dose of GWP42003-P. Remaining assessment visits and activities as determined by the investigator can still proceed as planned.

Reasons for removal from study intervention or procedural assessments include any of the following:

- Decision by the investigator.
- Decision by sponsor.
- Decision by regulatory authority.
- Withdrawal of parent(s)/LAR consent.
- Change in compliance with any inclusion/exclusion criterion that is clinically relevant and affects participant safety, as determined by the investigator (or designee).
- Protocol deviation that is considered to potentially compromise the safety of the participant.

- Noncompliance with study intervention.
- Noncompliance with any of the study assessments.
- Any clinically relevant sign or symptom that in the opinion of the investigator (or designee) warrants participant removal from study intervention.
- Liver Chemistry – Discontinuation of study intervention for abnormal liver tests is required by the investigator when a participant meets one of the following conditions outlined or in the presence of abnormal liver chemistries not meeting protocol-specified stopping rules if the investigator believes that it is in best interest of the participant.

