  - ALT or AST  $> 3 \times$  ULN with the appearance of fatigue, nausea, vomiting, right upper quadrant pain or tenderness, fever, rash, and/or eosinophilia ( $> 5\%$ ).
  - ALT or AST  $> 8 \times$  ULN.
  - ALT or AST  $> 5 \times$  ULN for more than 2 weeks.
  - ALT or AST  $> 3 \times$  ULN **and** (TBL  $> 2 \times$  ULN **or** INR  $> 1.5$ ).

Note: Prior to treatment discontinuation for the transaminase elevations noted above, the investigator may choose to confirm the transaminase elevations by repeating the following laboratory tests, tests within 24 to 48 hours: ALT, AST, TBL, INR, % eosinophils, gamma-glutamyl transferase (GGT), and alkaline phosphatase (also refer to [Section 12.7](#)). **Should the above transaminase elevation criteria be confirmed, the participant must permanently discontinue the study intervention. In cases where transaminase elevation withdrawal criteria are not met or confirmed, the dose of study intervention or a concomitant medication with known hepatotoxicity may be reduced following discussion with the medical monitor. The final decision regarding dose adjustments should be taken by the investigator.**

- Disease progression that compromises the ability of the participant to safely continue study intervention to the participant in the study.
- Participants who are withdrawn for nondrug related reasons may be replaced following discussion between the investigator and the sponsor. Participants withdrawn as a result of AEs thought to be related to study intervention, as determined by the investigator, will generally not be replaced. The decision regarding the replacement of participants will be documented.

The participant may also be permanently discontinued from treatment for any of the following:

- Participant or parent(s)/LAR noncompliance.
- AE (including clinically significant laboratory result) which, in the opinion of the investigator, would compromise the continued safe participation of the participant in the study.
- Did not meet eligibility criteria.

- Any evidence of drug abuse or drug diversion.
- Disease progression that compromises the ability of the participant to safely continue participating in the study.

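### For raised ALT/AST with raised bilirubin, Protocol 10.1 and 12.7 set different deadlines for the repeat tests, and 9.1.10.1 points to the wrong section for liver injury

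*Protocol*

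**What the plan says.** Four parts of the protocol deal with abnormal liver tests.

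- **Section 10.1** (repeated in the synopsis under Criteria for Withdrawal) lists four liver criteria. Its default is to stop: "Discontinuation of study intervention for abnormal liver tests is required by the investigator when a participant meets one of the following conditions". One criterion is ALT or AST > 3 × ULN together with either TBL > 2 × ULN or INR > 1.5. A note then allows confirmation before stopping: "the investigator may choose to confirm the transaminase elevations by repeating the following laboratory tests, tests within 24 to 48 hours". The sentence containing that permission ends by referring the reader to Section 12.7.
- **Section 12.7** repeats the four criteria and requires results meeting any of them to reach the sponsor within 24 hours of awareness, with the baseline results. For transaminase elevation with concurrent TBL elevation it adds a duty: "The investigator will arrange for the participant to return to the investigational site as soon as possible (within 24 hours of notice" of the abnormal results. Permanent discontinuation follows "if the above transaminase elevation criteria are confirmed by the first set of follow-up laboratory tests".
- **Section 9.1.10.1**, on laboratory sampling, directs the reader elsewhere: "For reporting and follow-up of potential cases of drug-induced liver injury, see [Section 12.6".
- **Section 12.6** is general adverse-event follow-up: "Adverse events considered related to the study intervention by the investigator or the sponsor should be followed up until resolution", or until the event is considered stable. It has no liver criteria and no deadline for repeat tests, and it leaves removal from treatment to the investigator's judgment.

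**The concern.** Sections 10.1 and 12.7 address the same decision: whether a participant with combined transaminase and bilirubin elevation must stop drug permanently. One makes the repeat optional with an outer limit of 48 hours; the other makes it mandatory within 24 hours and adds a history and physical examination. No text says which prevails. A site working from 10.1 or the synopsis can therefore comply with that text and still breach 12.7.

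The cross-reference in 9.1.10.1 makes this worse, because a site reviewing a laboratory report would naturally look there. The section it names contains neither the 24-hour return nor the 24-hour submission of results to the sponsor.

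These are operative safety instructions for children under 2 years of age, and the protocol itself says: "Serious side effects include hepatocellular injury". There is also a small reporting consequence. SAP 7.2 classifies deviations as important or non-important before database lock and lists them all, so the sponsor needs one rule to decide whether a late repeat is a deviation.

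**Working it through.** The plan gives no figure to reproduce. The check sets the texts side by side for the case of ALT/AST > 3 × ULN with TBL > 2 × ULN.

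| | 10.1 and synopsis | 12.7 |
|---|---|---|
| Status of repeat | optional | mandatory |
| Time limit | within 24 to 48 hours | within 24 hours |
| Clock starts | not stated | notice of abnormal results |
| Tests | ALT, AST, TBL, INR, % eosinophils, GGT, alkaline phosphatase (7) | the same 7 |
| Also required | nothing further in the note | history and physical examination |
| If confirmed | permanent discontinuation | permanent discontinuation |

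**Which repeat times conflict.** Assume both clocks start at notice of results, and let t be the hours from notice to the repeat.

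- t ≤ 24: satisfies both.
- 24 < t ≤ 48 (for example, 36 hours): complies with 10.1, breaches 12.7.
- t > 48: outside both limits.
- Drug stopped and no repeat: complies with the 10.1 note, breaches 12.7.

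The conflict window is 48 − 24 = 24 hours.

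**Sensitivity to the assumed clock.** Section 10.1 gives no start point. If its clock starts at the blood draw, and notice comes d hours later, its limit falls 48 − d hours after notice. The window is then 24 − d hours, and it closes once d reaches 24. If the 10.1 clock starts after notice, the window exceeds 24 hours. The documents give no laboratory turnaround time, so d is unknown.

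**Scope.** The 24-hour return in 12.7 is tied to concurrent TBL elevation. Elevation of transaminases > 3 × ULN alone, or of TBL > 2 × ULN alone, is followed up within 72 hours. The timing conflict therefore concerns one of the four criteria, and within it the TBL branch and not the INR branch.

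**Cross-reference.** Section 9.1.10.1 names 12.6. The section titled and written for drug-induced liver injury is 12.7, and 10.1 already points there. This error reaches further than the timing conflict, because the 24-hour submission to the sponsor in 12.7 covers all four criteria.

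**The case against.** The strongest reply is that the sections can be read together. The 10.1 note is a general permission across four criteria, and 12.7 adds a stricter rule for one branch. The sentence giving the longer limit also sends the reader to 12.7, so a careful site would follow 12.7. The duty to send results to the sponsor within 24 hours brings in a second reader before 48 hours have passed. The wrong pointer lands on the section immediately before the right one. Most of this stands, and it is why the severity is low. It does not remove the defect: a site that never reaches 12.7 misses the sponsor-submission duty too, and a precedence that must be inferred should be written down.

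A reader might infer two mutually exclusive windows, with 10.1 requiring the repeat to wait at least 24 hours. The text does not support that. It says within, which reads as an upper limit, so a prompt repeat satisfies both sections.

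A reader might also infer that a site stopping drug under 10.1 would abandon liver follow-up. Nothing in 10.1 says so. It calls for an early termination visit and a safety follow-up visit, and 9.1.10.1 requires clinically significant results to be recorded as adverse events and followed up. What could be missed is the specific 24-hour reassessment in 12.7.

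**Conclusion.** The concern holds as an internal inconsistency of low severity; it is not a flaw in the design. For transaminases > 3 × ULN with TBL > 2 × ULN, a repeat between 24 and 48 hours is allowed by 10.1 and forbidden by 12.7, on the assumption that both clocks start at notice. The 12.6 reference in 9.1.10.1 is wrong however the timing text is read.

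A reader might turn the 24-hour difference into extra drug exposure. At twice-daily dosing, 24 / 12 = 2 doses: 2 × 5 = 10 mg/kg at the 10 mg/kg/day target, and, with the maxima in 8.1.2 ("20 mg/kg/day (10 mg/kg b.i.d.) for LGS and DS or 25 mg/kg/day (12.5 mg/kg b.i.d.) for TSC"), 2 × 10 = 20 mg/kg and 2 × 12.5 = 25 mg/kg. The documents do not support these as a measure of harm. They require a common clock that 10.1 does not state, and dosing that continues while confirmation is awaited. The default in 10.1 is to stop, in which case the conflict adds no exposure. Neither section tells the site to hold drug pending the repeat, so that gap is not specific to 10.1.

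No estimate, summary or SAP liver listing (SAP 9.2.1) changes; at most the status of an entry in the deviation listing does. The decision of 28 January 2025 to terminate the study (SAP 1 and 9.6) limits urgency. The documents do not say whether any participant remains on drug or in follow-up.

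**What to change.** 1. In 10.1 and in the synopsis, add one sentence after the confirmation note: for ALT or AST > 3 × ULN with TBL > 2 × ULN, the mandatory return within 24 hours of notice in Section 12.7 governs, whether or not study drug has already been stopped.
2. In 9.1.10.1, change the reference for drug-induced liver injury from Section 12.6 to Section 12.7.

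The cost is one sentence in each of two places and one corrected section number, with no new tests and no SAP change. If any participant is still in follow-up, a clarification letter would do. Otherwise the correction serves the description of liver follow-up in the abbreviated study report and any reuse of this text. The change does not tell sites whether to hold drug while the repeat is awaited; that clinical question is for the sponsor's medical team.

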## **12.8. Notification of Safety Information to Investigators, Regulatory Authorities, and IRBs/IECs.**

In accordance with the Regulation (EU) 536/2014, relevant parts of the FDA Code of Federal Regulations and any national regulations, the sponsor will inform investigators, regulatory authorities, and relevant IRBs/IECs of all relevant safety information. This will include the reporting of relevant SAEs and all Suspected Unexpected Serious Adverse Reactions (SUSARs). In the EU, submission of expedited safety reports to Eudravigilance will be performed via E2B.

This information will be provided through 2 sources:

1. Investigator's Brochure: a compilation of the clinical and non-clinical safety data available on the study intervention that is relevant to the trial. The Investigator's Brochure is updated annually or when important new safety information becomes available.
2. Council for International Organizations of Medical Sciences (CIOMS) reports: these reports are issued every time a SUSAR is reported to the sponsor. They provide information on individual case reports and are sent to all the regulatory authorities, the relevant central IRB/IEC that have approved the trial and investigators. As required, the investigator should notify their regional IRBs/IECs of SAEs or SUSARs occurring at their site and other AE reports, i.e., CIOMS reports and any additional safety documentation received from the sponsor, in accordance with local procedures.

In the United States, investigators are normally required to report promptly to their IRBs/IECs all unanticipated problems involving risks to participants, or others, including AEs that should be considered unanticipated problems. Based on current FDA guidance the following clarification is provided in determining what constitutes an unanticipated problem:

In general, an AE observed during the conduct of a study should be considered an unanticipated problem involving risk to participants and reported to the IRB/IEC, *only* if it were unexpected, serious, and would have implications for the conduct of the study (e.g., requiring a significant, and usually safety-related, change in the protocol such as revising inclusion/exclusion criteria or including a new monitoring requirement, informed consent, or IB). An individual AE occurrence *ordinarily* does

not meet these criteria because, as an isolated event, its implications for the study cannot be understood.

The FDA guidance states that, accordingly, to satisfy the investigator's obligation to notify the IRB/IEC of unanticipated problems, any investigators participating in a multicentre study may rely on the sponsor's assessment and provide to the IRB/IEC a report of the unanticipated problem prepared by the sponsor.

The sponsor will inform investigators, regulatory authorities and relevant IRBs/IECs of any safety issues or case reports that are considered to be unanticipated and provide such reports as mentioned above. It should be noted that a single SUSAR report notified to investigators in the study does not necessarily constitute an unanticipated problem unless identified by the sponsor in the submission cover letter.

As a minimum, the recipient will be sent all of the above and relevant updates between the period from ethical approval and final database lock.

